#### **• Secondary Objectives:**

- To assess safety and acute toxicity of SBRT followed by prostatectomy. This will be based on CTCAE version 4.0 and patient reported quality of life (EPIC and IPSS questionnaires).
- Investigation of the radiobiology of SBRT in prostate cancer using resected prostate tumor tissue. For the correlative genomic analyses, prostate lesions at the time of prostatectomy will be processed for RNA and exome sequencing and compared to existing sequencing data for localized prostate cancers. We will utilize both supervised and unsupervised analyses of

- Pathway activation from RNA-seq data sets in order to determine which pathways are enriched after irradiation.
- Evaluation of the nature of the immune response to prostate cancer generated by SBRT.
    - Systemic immune response. Blood that is collected pre SBRT, between 0 and 4 weeks after SBRT, and at 3 and 6 month intervals after SBRT will be assessed as follows: PBMCs will be isolated over Ficoll-gradients and stored frozen until analysis. Lymphoid and myeloid subset phenotyping will be assessed by antibody staining and multi-color flow cytometry (LSR-Fortessa, BD). Circulating cytokines, PGE2, prostate-tumor specific antibodies, HMGB-1 protein and the tryptophan/kynurenine ratio in plasma will be quantified by ELISA. Tumor-specific CD4 and CD8 T cell activities to known HLA-matched, immunodominant, tumor-associated antigens will be assessed ex vivo by IFN  $\gamma$  -ELISPOT and dextramer staining. The tumor antigens of choice will include PSA and PSMA.
    - Local immune response. The immune response at the tumor site will be visualized through immunohistochemistry (IHC), with particular focus on T cells (CD3+), T regulatory cells (CD4+ CD25hi), tumor infiltrating myeloid-derived suppressor cells (CD11b+ Gr-1+ CD15+) and tumor-associated macrophages (CD11b+F4/80+). Levels of CSF1/CSF1R, tumor MHC I, PD-1 and PD-L1 are also of interest as are markers for EMT (vimentin, N-cadherin, E-cadherin), for neuroendocrine differentiation (chromogranin A, neuron specific enolase), AR protein and p53. Comparisons will be made to pre-treatment biopsy material when possible and to tissue microarrays of non-irradiated prostatectomy specimens.

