**Follow-up:**

- 0 to 4 weeks after the final fraction of radiation, patients will have approximately 60 mLs of blood drawn for serum translational biomarker research. Patients will also be evaluated by their physician and Adverse Events and Concomitant Medications will be assessed. EPIC and IPSS questionnaires will also be administered at this time.
- Patients are followed every three months ( $\pm$  4 weeks) for one year post surgery. At each follow-up visit, patients are evaluated for CTCAE (version 4.0) toxicity scores, and the EPIC and IPSS questionnaires will be administered. Blood draws (~5 mLs) to assess PSA are drawn at each of the follow-up visits unless PSA lab evaluations have already been done within 4 weeks of the study visit. In addition, at the 3 month and 6 month follow-up visits, approximately 60 mLs of blood will be drawn for serum translational biomarker study. After one year of follow-up, patients will be seen as per routine care.

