**OUTCOME MEASURES**

**Primary objective, feasibility:** A patient is considered to have completed treatment if they received the prescribed radiation dose of 24 Gy delivered in 3 fractions of 8 Gy within a span of 2 weeks and subsequently undergo prostatectomy within 4 weeks of completing radiotherapy.

**Secondary objective, safety and acute toxicity:** Patients will be evaluated during RT, prostatectomy, and at intervals of 3 months following completion of treatment for one year. At each visit, patients will complete the EPIC and IPSS questionnaires and will be assessed for CTCAE v4 toxicities.

**Secondary objective, correlative studies:** Assessments of the systemic immune response will utilize blood that is collected pretreatment, after completion of SBRT, and at 3 and 6 months post treatment completion. The local immune response (intratumoral) will utilize the resected prostatectomy specimen, pre-treatment biopsies, and archived tissue arrays of prostatectomy specimens that did not undergo RT. RNA- and exome-sequencing of irradiated prostate tumors will utilize the resected prostatectomy specimens, which will be compared to existing sequencing analyses of localized prostate cancers (TCGA) matched for histology and Gleason grade.

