## STATISTICAL CONSIDERATIONS

**Feasibility and sample size determination.** Our primary objective is to determine feasibility of preoperative adjuvant stereotactic body radiotherapy for patients who are at high risk of local failure after prostatectomy. A confidence interval approach is used to estimate the sample size appropriate for this feasibility study (24, 25). We consider preoperative adjuvant stereotactic body radiotherapy feasible when the estimated treatment completion rate for an enrolled patient is at least 75%. For a two-sided 90% exact binomial confidence interval, a sample size of 12 patients yields a lower limit of the 90% confidence interval of at least 75% if the true proportion of patients completing treatment is 93%. A feasibility assessment of preoperative adjuvant stereotactic body radiotherapy is a required step prior to designing a larger trial.

**Estimation of eligible patients and enrollment.** Numbers of eligible patients are estimated based on projected patient populations. Eligible patients for the study are drawn from prostate cancer patients referred for treatment evaluation at UCLA Medical Center by the study investigators. This is anticipated to be 200 patients in 2016. At least 25% are anticipated to be eligible based on the risk classification of patients for our protocol (patients at high risk of recurrence). We estimate 75% of these patients will be surgical candidates. Standard treatments for these patients include either surgery (that includes adjuvant radiotherapy with or without androgen deprivation therapy) or definitive radiotherapy with concurrent androgen deprivation therapy. We estimate 40% of the patients will elect definitive radiotherapy with androgen deprivation. Of the remaining 60% of eligible patients, we anticipate that between 20 and 50% would be amenable to preoperative adjuvant radiotherapy. Our study is planned to accrue patients within three years. Therefore, there are sufficient numbers of patients eligible to participate in this study.

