**Measurements of serological markers (secondary objective).** Circulating cytokines, PGE2, prostate-tumor specific antibodies, HMGB-1 protein and the tryptophan/kynurenine ratio in plasma will be quantified by ELISA. Tumor-specific CD4 and CD8 T cell activities to known HLA-matched, immunodominant, tumor-associated antigens will be assessed ex vivo by IFN $\gamma$ -ELISPOT and dextramer staining. The tumor antigens of choice will include PSA and PSMA. A repeated measures analysis of variance will be used to assess differences in these serological markers over time. In addition to the overall time effect in the ANOVA model, we plan to test specific contrasts

between serological markers pre-treatment (baseline) and the first measurement post SBRT (pre surgery), where we anticipate to observe an increase in circulating tumor-specific CD4 and CD8 T cell activity.

Multivariate profile analyses may be used when patterns for various markers emerge. These statistical analyses will be performed using IBM SPSS Statistics for Windows, Version 20.0. (Armonk, NY) statistical software.

**Measurements of intra-tumoral and intra-prostatic markers (secondary objective).** The immune response at the tumor site will be visualized through immunohistochemistry (IHC), with particular focus on T cells (CD3+), T regulatory cells (CD4+ CD25hi), tumor infiltrating myeloid-derived suppressor cells (CD11b+ Gr-1+ CD15+) and tumor-associated macrophages (CD11b+F4/80+). Levels of CSF1/CSF1R, tumor MHC I, PD-1 and PD-L1 are also of interest as are markers for EMT (vimentin, N-cadherin, E-cadherin), for neuroendocrine differentiation (chromogranin A, neuron specific enolase), AR protein and p53. IntMax (scale of 0-300) = (% of positive tumor cells [scale of 0-100]) X (intensity of staining based on 0-3 scale [scale of 0-3]) will be assessed for each marker. Comparisons in markers will be made between: 1- post SBRT prostatectomy specimens vs biopsy material pre-SBRT; and 2- post SBRT prostatectomy specimens vs archival tissue of prostatectomy specimens (that did not undergo RT).

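### The repeated measures ANOVA of the blood markers has no missing-data rule and, run conventionally, would drop a patient with both early draws who lacks a 3- or 6-month draw from the pre/post-SBRT contrast

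*Combined protocol and SAP*

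**What the plan says.** The Statistical Considerations, under the measurements of serological markers, name one definite method: "A repeated measures analysis of variance will be used to assess differences in these serological markers over time". The plan then turns to the comparison of most interest: "In addition to the overall time effect in the ANOVA model, we plan to test specific contrasts". The paragraph sets these out as comparisons "between serological markers pre-treatment (baseline) and the first measurement post SBRT (pre surgery"). A rise in tumor-specific CD4 and CD8 T cell activity is expected there. Multivariate profile analyses are mentioned as a possibility. On software the text says "These statistical analyses will be performed using IBM SPSS Statistics for Windows, Version 20.0", without naming a procedure.

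The four draws are before SBRT, 0 to 4 weeks after it, and at 3 and 6 months. The later two are timed in three ways:

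- Secondary Objectives, from SBRT: "Blood that is collected pre SBRT, between 0 and 4 weeks after SBRT, and at 3 and 6 month intervals after SBRT".
- Follow-up, at visits counted from surgery: "In addition, at the 3 month and 6 month follow-up visits, approximately 60 mLs of blood will be drawn".
- Outcome Measures, from the end of treatment: "blood that is collected pretreatment, after completion of SBRT, and at 3 and 6 months post treatment completion".

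The documents give no missing-data rule, no analysis set for the markers and no separate paired test for this contrast. For the tissue markers, by comparison, a paired t-test or signed-rank test is named.

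**The concern.** In its conventional form, repeated measures ANOVA works on one complete row per patient, so one missing draw removes the whole patient. The pre/post-SBRT contrast needs only draws 1 and 2. If it is taken from the four-draw model, a patient who gave both early samples is discarded because a sample was not taken months later.

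Such a gap is foreseeable. The trial is about whether irradiated patients reach surgery in time. If the later draws are counted from surgery, as under Follow-up, a patient who is irradiated but never operated on has no defined 3- or 6-month draw. A patient who completes treatment and simply misses a later visit is lost in the same way.

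At stake is precision on the one directional marker hypothesis in the statistical section, in a trial of 12 patients.

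**Working it through.** **The plan's own figure.** There is none to reproduce. The marker analysis states no sample size, effect, SD, alpha, power or dropout rate.

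**Inputs from the documents.** 12 patients; four draws; an assumed true completion rate of 93%; and a floor at which treatment is called "feasible when the estimated treatment completion rate for an enrolled patient is at least 75" percent.

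**Assumptions of this check.** Two-sided 5% test; an effect chosen to give 80% power with 12 patients; and, for steps 1 and 2, that each non-completer has both early draws and lacks a later one. That last assumption gives the most that non-completion can cost the contrast.

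**Step 1: patients lost.** Expected loss = 12 × (1 − completion rate).

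- At 93%: 12 × 0.07 = 0.84. Chance of at least one non-completer: 1 − 0.93^12 = 0.58.
- At 75%: 12 × 0.25 = 3.0. Chance of at least one: 1 − 0.75^12 = 0.97.

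**Step 2: effect on the paired contrast.** With n pairs and a mean change of d SDs of the paired difference, the noncentrality is d√n on n − 1 degrees of freedom. The 95% half-width is t(0.975; n − 1)/√n. With d = 0.889:

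| Pairs | Noncentrality | Power | Half-width (SD) | SE relative to n = 12 |
|---|---|---|---|---|
| 12 | 3.08 | 0.80 | 2.201/√12 = 0.635 | 1 |
| 11 | 2.95 | 0.76 | 2.228/√11 = 0.672 | √(12/11) = 1.04 |
| 9 | 2.67 | 0.65 | 2.306/√9 = 0.769 | √(12/9) = 1.15 |

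**Step 3: draws missed for any reason.** If draws are missed independently (assumed), the expected number with all four is 12p^4 and with the first two 12p^2.

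- p = 0.95: 12 × 0.95^4 = 9.8, against 12 × 0.95^2 = 10.8.
- p = 0.90: 12 × 0.90^4 = 7.9, against 12 × 0.90^2 = 9.7.

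The fair comparator at 90% availability is 9.7, not 12, because no method recovers a missing early draw.

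**Step 4: what a mixed model recovers.** Take between- and within-patient SD 1, a true change of 1.0, and 3 of 12 patients without later draws (all assumed). The paired difference has SD √2, so the standard error should be √2/√9 = 0.471 on complete cases and √2/√12 = 0.408 on all pairs. In 600 simulated trials with a random-intercept model fitted by REML:

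- Early draws present, loss unrelated to response: complete cases averaged 0.97 (SD 0.476), the mixed model 0.99 (SD 0.422).
- Only a baseline draw present: SD 0.464 for the mixed model against 0.476. Almost nothing is gained.
- The three smallest changes lost (an extreme assumption): complete cases averaged 1.55, the mixed model 0.99.

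Some mixed-model fits gave convergence warnings, which bears on the choice of covariance below.

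**The case against.** **Non-completion is not a missing draw.** This is the strongest objection, and it stands. A reader might infer that every patient who fails to complete treatment leaves the contrast. The documents do not support that. Completion requires 24 Gy within 2 weeks and surgery within 4 weeks of radiotherapy, so a patient operated on in week 5 is a non-completer who can still give all four draws. Nothing says that non-completers stop giving blood. Under the Secondary Objectives wording, an unoperated patient still has 3- and 6-month draws. A patient who does not finish SBRT may have no post-SBRT draw, and then no method helps.

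**Deletion is inferred, not stated.** This also stands in part. The SPSS procedure is not named, and the phrase about the ANOVA model attaches grammatically to the overall time effect. Testing the contrast on available pairs is not excluded. Even so, the in-model reading is the natural one, and the text leaves the choice open.

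**Sphericity and selection bias.** A reader might infer that uneven spacing breaks the ANOVA, or that complete cases are a biased subset. Neither is established. Spacing is irrelevant when time is categorical, a two-time contrast tested on its own differences needs no sphericity, and the profile analyses that the plan allows do not assume it. Bias appeared only when the smallest responders were deliberately removed.

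**The remedy is partly preference.** With complete data and matching covariance assumptions the two methods give essentially the same contrast, and a paired test on draws 1 and 2 alone would solve the narrow problem. That is fair. The mixed model's further merit is that it also uses partial data for the overall time effect.

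**Conclusion.** The point holds in a limited form. The plan names a complete-case method, as conventionally run, for a contrast that does not need complete cases, and gives no missing-data rule. A patient with draws 1 and 2 but no later draw would be lost for no statistical reason.

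The size is modest. Non-completion costs at most about 0.8 patients on average at the plan's assumed completion rate; losing one patient takes power from 80% to 76%. Nine patients and 65% power is the worst case at the feasibility floor, and a reader should not take it as the expected outcome. Missed later draws among completers can add to the loss, as the 7.9 against 9.7 comparison shows. All the power figures rest on an effect size and alpha that the plan does not state.

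The analysis is secondary and correlative. This is a worthwhile, inexpensive improvement, not a flaw that threatens the trial.

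**What to change.** In the serological markers paragraph, replace the repeated measures ANOVA with a linear mixed model on all available draws: visit as a categorical fixed effect, a parsimonious within-patient covariance such as a random intercept, REML, and small-sample degrees of freedom (for example Satterthwaite). An unstructured covariance over four visits would have 4 × 5/2 = 10 parameters, too many for 12 patients. Take the baseline versus first post-SBRT contrast from this model so that every patient with both draws contributes, and report a paired test on draws 1 and 2 as a check that does not depend on the covariance model.

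State the marker analysis set and whether patients who are not operated on are still to be drawn at 3 and 6 months. Reconcile the timing of those draws across Secondary Objectives, Follow-up and Outcome Measures.

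The cost is a few sentences and slightly more analysis work. The downsides are reliance on missing-at-random and an approximate covariance model in 12 patients. Patients without a post-SBRT draw will still add almost nothing to the contrast.

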In vitro and in vivo work has suggested that high dose per fraction RT alters the extent and the type of damage to DNA and to vascular structures including endothelial cells, and it seems to generate stronger anti-tumor immunity. We already know that irradiation generates an immunogenic cancer cell death, in part by inducing genetic programs that signal “danger” to the immune system (6). SBRT may therefore drive immune recognition and tumor immunity of potentially systemic proportions (8). It starts with the generation of a pro-inflammatory microenvironment with up-regulation of MHC and co-stimulatory molecules that can enhance tumor antigen cross-presentation by dendritic cells and that broadens the antigenic repertoire. Progenitor cells of mesenchymal, endothelial, myeloid and lymphoid origin get mobilized to infiltrate the irradiated area. What is important here is that according to preclinical evidence, doses considerably higher than the conventional 1.8-2 Gy are required to generate high enough levels of pro-inflammatory cytokines and superior anti-tumor responses. Based on our experience with clinical and pre-clinical tumor models, we hypothesize that pre-operative, prostate SBRT with 3 fractions of 8 Gy given over a relatively short time will lead to measurable immunological changes, locally and systemically. Understanding these changes could inform the use of immunomodulatory therapies in locally-advanced as well as metastatic prostate cancer. Unfortunately, the same pro-inflammatory conditions may drive reprogramming towards a more resistant cancer stem cell phenotype that could increase the likelihood of recurrence in high-risk patients. The balance between these forces and their correlation, if any, in individual high-risk patients will be investigated.

The translational component of this trial seeks: 1. To investigate the radiobiology of SBRT in prostate cancer using resected prostate tumor tissue, and 2. To evaluate the nature of the immune response to prostate cancer generated by SBRT. These aims are included within the secondary objectives of this trial.

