## Eligibility Criteria

- Histologically confirmed primary non-metastatic adenocarcinoma of the prostate
- Patient desires and is medically fit to undergo prostatectomy
- Age  $\geq$  18
- KPS  $\geq$  70
- Patients on ADT are allowed
- For confirmation of high risk local failure status, patients will have any one of the following:
  - CT or MRI demonstrating SVI or EPE within 1 year of enrollment into the study
  - Pre-biopsy PSA  $\geq$  20
  - Gleason score 7-10 (Gleason 7 must be 4+3), presence of any Gleason 5 (even if a tertiary score) as determined at diagnostic biopsy

- Gleason score 7 and >50% of biopsy cores positive for prostate cancer
  - Clinical stage  $\geq$  T3 (staging by imaging acceptable)
- An image-guided biopsy (via Artemis Ultrasound with MRI co-registration) is encouraged but not required if not performed as standard of care biopsy

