For comparison between post SBRT prostatectomy specimens and biopsy material pre-SBRT, average IntMax will be compared using a paired t-test or Wilcoxon signed-rank test (if the IntMax scores do not follow a normal distribution). For comparison between post SBRT prostatectomy specimens and archived material, average IntMax will be compared using a t-test or Wilcoxon rank-sum test (if the IntMax scores do not follow a normal distribution).

**RNA and DNA exome sequencing (secondary objective).** Quality control will be performed on the raw sequence data from RNA-seq experiments, which contain multiple short-read sequences with Phred quality score information using FastQC and FASTX-Toolkit. Bowtie2 will be used to align reads, which will then be mapped to the reference genome by TopHat2. Raw reads from exome sequencing will be aligned via BWA and converted to BAM format, and processed with the Genome Analysis Toolkit software package. Comparisons will be made to existing sequencing data (TCGA) for localized prostate tumors matched for histology and Gleason grade. Functional annotation will be performed using Gene Ontology, KEGG, and Reactome.

**Stopping Rules for Toxicity.** Prior studies evaluating RT prior to prostatectomy demonstrate safety of pre-operative RT at doses of up to 54 Gy in 30 fractions (12). It is anticipated that toxicity in this study will be low because our dose is selected based on the prior studies.

Nevertheless, our trial will be stopped for toxicity if any treatment related toxicity of CTCAE v4.0 grade 3 or above is observed in more than two subjects during the study

period in the following categories: gastrointestinal, urinary, with the exception of temporary use of a catheter and urinary incontinence, which can occur after prostatectomy in the absence of radiotherapy.

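### Two of the four infiltrating-cell populations in the IHC focus are defined with mouse markers (Gr-1, F4/80), although all the tissue to be stained is human

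*Combined protocol and SAP*

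**What the plan says.** The Statistical Considerations section, in its paragraph on intra-tumoral and intra-prostatic markers, sets out the IHC work "with particular focus on T cells (CD3+), T regulatory cells (CD4+ CD25hi", and then adds "tumor infiltrating myeloid-derived suppressor cells (CD11b+ Gr-1+ CD15+) and tumor-associated macrophages (CD11b+F4/80". The local immune response item under Secondary Objectives gives the same four definitions in the same terms.

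Outcome Measures identifies the tissue: "The local immune response (intratumoral) will utilize the resected prostatectomy specimen, pre-treatment biopsies, and archived tissue arrays". The archived arrays come from prostatectomies without radiotherapy. The patients are men with prostate cancer; the first entry criterion is "Histologically confirmed primary non-metastatic adenocarcinoma of the prostate".

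Each marker is to receive an IntMax score, the percentage of positive cells multiplied by staining intensity. Two comparisons follow: "post SBRT prostatectomy specimens vs biopsy material pre-SBRT", and the same specimens against unirradiated archival tissue. For the first, "average IntMax will be compared using a paired t-test or Wilcoxon signed-rank test". The second uses the unpaired counterparts.

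**The concern.** Gr-1 is the mouse Ly-6G/Ly-6C antigen and has no direct human counterpart. F4/80 is the mouse macrophage antigen; it has a human homologue, but that homologue is not an accepted marker of human macrophages. A panel built on these two markers and applied to human prostate does not measure the cells it names.

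What is at stake is the part of the local immune-response objective that concerns myeloid cells in the tumor. If the plan is followed as written, the two planned comparisons say nothing about whether MDSC or macrophages change after SBRT. If the laboratory changes antibodies on its own initiative, the panel is no longer prespecified and may differ between biopsies, trial specimens and archival arrays. The paired material is limited: there are 12 patients, and the secondary objectives promise comparison with biopsy only where possible.

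**Working it through.** No power, alpha or effect-size figure bears on this point, and the plan states none for the IHC comparisons. The check sets the marker definitions beside the tissue sources.

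1. **Definitions.** From Secondary Objectives and Statistical Considerations, which agree:
   - T cells: CD3+
   - T regulatory cells: CD4+ CD25hi
   - MDSC: CD11b+ Gr-1+ CD15+
   - Tumor-associated macrophages: CD11b+ F4/80+

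2. **Count.** The definitions containing Gr-1 or F4/80 are MDSC and macrophages: 2 of 4, or 50% of the named populations.

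3. **Tissue.** Outcome Measures, the Prostatectomy section and Statistical Considerations give three sources: the trial prostatectomy specimen, the pre-SBRT biopsy and archived unirradiated prostatectomy tissue. All three are human. No section describes animal tissue.

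4. **Possible rescue elsewhere in the text.** No section gives antibody clones, human equivalents of Gr-1 or F4/80, or another MDSC or macrophage definition for tissue. The myeloid phenotyping by flow cytometry is done on blood and lists no markers, so it does not supply the tissue measure.

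5. **Consequence.** Both definitions require all their markers together. With no valid Gr-1 or F4/80 reading in human tissue, neither population can be identified as specified. CD11b and CD15 do stain human tissue and can be scored, but neither marker alone, nor the pair, is the phenotype that the plan names.

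6. **Antibody count for a repair.** The plan lists four distinct antibodies for these two populations: CD11b, Gr-1, CD15, F4/80. Replacing Gr-1 by CD33 and F4/80 by CD68 gives CD11b, CD33, CD15, CD68, which is again four. Adding CD163 makes 4 + 1 = 5.

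The point does not depend on how IntMax is scored. The formula refers to positive tumor cells, which is a separate matter for infiltrating cells; correcting it would not make these two populations detectable.

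**The case against.** The strongest objection is that the documents nowhere state which species a marker belongs to, so the plan does not contradict itself. That is true. The step rests on basic immunology nomenclature, which needs no particular study to support it. It stands as a stated premise.

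A second objection is that a laboratory would notice at antibody validation and substitute. It may well, but the substitution would then be undocumented and not fixed in advance across the three tissue sources.

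Three stronger readings are tempting and are not supported:

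- **A reader might infer that MDSC positivity would be recorded as zero everywhere, so that both comparisons are zero against zero and read as no effect of SBRT.** The plan scores IntMax marker by marker and defines no co-expression count, so a zero for the combined phenotype is not a specified output. Nonspecific staining, a missing assay or a substitution are all possible. What can be said is that no valid measure results.
- **A reader might infer that the central translational question, immunity against resistance, is lost.** The background sections that raise it do not name MDSC or macrophages as its test. Resistance there is stem-cell reprogramming, EMT and neuroendocrine change, and the EMT and neuroendocrine markers in the IHC plan are untouched. Blood myeloid subsets, CSF1/CSF1R staining and RNA sequencing do not use these definitions either.
- **A reader might infer that the panel was carried over from mouse experiments.** The background does introduce its immune hypothesis with "Based on our experience with clinical and pre-clinical tumor models", but that sentence names no marker and does not show where the definitions came from.

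**Conclusion.** The concern holds in a limited form. Two of the four infiltrating-cell populations given particular attention in the IHC are defined with mouse markers and cannot be validly measured in human tissue as specified. Both planned comparisons, with biopsy and with archival tissue, would be uninformative for those two populations.

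The conclusion rests on two things: the documents' own text, which shows that all the tissue is human and that no alternative definition is given, and the general nomenclature that Gr-1 and F4/80 are mouse markers.

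Severity is minor. Only an exploratory part of a secondary objective is affected. The completion-rate endpoint, the 12 patients, the toxicity stopping rule, the T-cell, checkpoint, EMT and neuroendocrine markers, and the blood assays all stand.

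**What to change.** Before any staining, replace Gr-1 and F4/80 with markers validated for IHC in human tissue, in the same words under Secondary Objectives and in Statistical Considerations. One workable example is CD33 alongside CD11b and CD15 for granulocytic MDSC, and CD68, with or without CD163, for macrophages. The choice belongs to the sponsor's laboratory; the documents do not dictate it. State that the same panel applies to trial specimens, pre-SBRT biopsies and archival arrays. Because MDSC are defined by joint expression and IntMax is scored per marker, the revised text should also say whether the markers are reported singly or in combination.

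The cost is new antibodies, their validation and a wording change. The antibody count stays at four with CD33 and CD68 and rises to five if CD163 is added. No patient procedure changes. If some staining has already been done, the Prostatectomy section provides for residual tissue to be kept indefinitely, so restaining of those specimens may be possible.

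### The only tissue score in the plan counts positive tumor cells, so it cannot measure infiltration by the four immune-cell populations that the IHC is meant to study

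*Combined protocol and SAP*

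**What the plan says.** Under STATISTICAL CONSIDERATIONS, the paragraph on intra-tumoral and intra-prostatic markers describes IHC at the tumor site, "with particular focus on T cells (CD3+), T regulatory cells (CD4+ CD25hi), tumor infiltrating myeloid-derived suppressor cells", and goes on to tumor-associated macrophages. It then lists further markers of interest: CSF1/CSF1R, tumor MHC I, PD-1, PD-L1, EMT and neuroendocrine markers, AR and p53. One score follows: "IntMax (scale of 0-300) = (% of positive tumor cells [scale of 0-100]) X (intensity of staining based on 0-3 scale"]. Its scope is unrestricted: it "will be assessed for each marker".

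Two comparisons are planned:
- Post-SBRT prostatectomy specimen against the patient's own pre-SBRT biopsy: "average IntMax will be compared using a paired t-test or Wilcoxon signed-rank test".
- Post-SBRT specimen against archived non-irradiated prostatectomy tissue: "average IntMax will be compared using a t-test or Wilcoxon rank-sum test".

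The Secondary Objectives section repeats the marker list without a score and adds: "Comparisons will be made to pre-treatment biopsy material when possible and to tissue microarrays of non-irradiated prostatectomy specimens". OUTCOME MEASURES names the tissue sources only. No section gives an immune-cell count, a density or any other tissue percentage.

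**The concern.** The percentage in the score is a percentage of tumor cells. The four populations named as the focus are immune cells that enter the tumor from outside. The protocol's own rationale, under Clinical - Translational Relevance, expects this: "Progenitor cells of mesenchymal, endothelial, myeloid and lymphoid origin get mobilized to infiltrate the irradiated area". A rule that looks only at staining on tumor cells cannot register the arrival of other cells.

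At stake is whether the tissue work can answer one of its stated questions: do immune cells enter the tumor after SBRT? Sequencing will carry some immune information, but it uses the resected specimens, "which will be compared to existing sequencing analyses of localized prostate cancers (TCGA) matched for histology and Gleason grade". IHC is therefore the only planned tissue comparison before and after SBRT within the same patient.

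**Working it through.** **Inputs from the documents.** Percentage of positive tumor cells (0 to 100), intensity (0 to 3), scope (every marker), and test variable (average IntMax in both comparisons), all from STATISTICAL CONSIDERATIONS. Sample size is 12 patients. The documents give no alpha, variance or intensity distribution for these tests.

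**The plan's own figure.** IntMax = percentage × intensity. Maximum 100 × 3 = 300; minimum 0. The stated range of 0 to 300 reproduces.

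**Reading 1: literal (percentage of tumor cells, all markers).**
- With 0% positive tumor cells, 0 × 0, 0 × 1, 0 × 2 and 0 × 3 are all 0, however many immune cells are present.
- If stray staining made 1% to 5% of tumor cells positive (an assumption), the ceiling would be 1 × 3 = 3 to 5 × 3 = 15 out of 300, and it would still not track the infiltrate.
- With 12 pairs of zeros, every difference is 0. The paired t statistic is 0/0 and undefined, and the signed-rank test has no non-zero difference to rank (p = 1). Against archived scores that are also all zero, the rank-sum test has only ties (p = 1).

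**Reading 2: narrow (the score is meant only for tumor-cell proteins).** The four focus populations then have no stated readout, and neither test has a variable to use for them.

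**Reading 3: loose (percentage of all cells in the tumor area).**
- The denominator is not stated: epithelium, stroma or both; all cells or nucleated cells.
- Number and intensity are confounded: 10 × 3 = 30 and 30 × 1 = 30, so a tripled infiltrate can show no change.
- If intensity is a constant c in every specimen, each score is c times the percentage. The t statistic and the ranks are then unchanged, and nothing is lost. The loss depends on how intensity varies between specimens, which the documents do not describe.

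**Check on a tempting remedy.** Suppose the readout were positive cells as a percentage of nucleated cells. Take 5 immune cells and 95 others per 100 (assumption), and let SBRT remove some of the others while immune-cell number stays fixed:
- 20% of others lost: 5 / (5 + 0.8 × 95) = 5 / 81 = 6.2%.
- 50% of others lost: 5 / (5 + 0.5 × 95) = 5 / 52.5 = 9.5%.

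The percentage nearly doubles in the second case with no immune cell added. The protocol itself gives genotoxic cell killing as a main effect of radiation (Scientific impact), so this denominator cannot be assumed stable. A count per unit area does not use it.

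**The case against.** The best case for the plan is that nobody would score CD3 on tumor epithelium. The marker paragraph speaks of myeloid cells that infiltrate the tumor and of an immune response at the tumor site, so the formula is probably a generic sentence written with tumor-cell markers in mind. On that view the gap is an unstated compartment that the pathologist would fill sensibly. This is a fair account of how the text arose, and it stands against one stronger inference: that the trial will in practice report scores near zero for these populations. The documents show only that the rule, read literally, would give that result. They do not show how slides will be read.

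It does not rescue the rule. The narrow reading leaves no readout and the loose one leaves a confounded score with no denominator. Choosing between them after the slides have been seen adds analytic freedom in a study of 12 patients.

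A reader might also infer a definite loss of power or an inflated false-positive rate. The documents support neither. Under the loose reading the loss can be nil, and any other figure needs assumed variances and intensity distributions. The example of 10% at intensity 3 against 30% at intensity 1 shows what the score permits, not what is likely.

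Finally, the weight is modest: this is correlative work, and the biopsy comparison is made only where material allows, so there may be fewer than 12 pairs. That limits the importance of the point but not its correctness.

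**Conclusion.** The point holds. As written, the tissue score cannot measure infiltration by any of the four named populations, in either planned comparison, and neither alternative reading supplies a usable readout. This follows from the definition and from the fact that these are not tumor cells; it needs no numerical assumption. The stray-staining ceiling of 3 to 15 out of 300 is illustrative only.

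The reach is limited to the local immune-infiltration part of a correlative secondary objective. The score remains suitable for markers read on tumor cells, such as tumor MHC I, the EMT and neuroendocrine markers, AR and p53. PD-1 and CSF1/CSF1R are affected only where the stain lies on other cells. The blood assays, the sequencing and the primary feasibility endpoint are unaffected, so it would be wrong to conclude that the immune objective as a whole fails. The text should be corrected before the slides are scored, but the point does not call the trial into question.

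**What to change.** In the marker paragraph of STATISTICAL CONSIDERATIONS:

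- Limit IntMax to markers scored on tumor cells.
- For the four immune populations, prespecify positive cells per mm² in a defined tumor region, without the intensity multiplier. State whether epithelium, stroma or both are counted. Average per patient and apply the paired and two-sample tests already planned.
- Treat any percentage of nucleated cells as supportive only, for the reason shown in the working.
- State which stain defines a counted cell. Three of the four populations are defined by two or three antigens; where co-positivity cannot be read from the planned stains, report single-marker counts and label them as such.
- State the scored compartment for PD-1 and CSF1/CSF1R.

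The cost is a few sentences and some extra counting on the same slides, with no new staining. Single-marker counts are less specific, and values from small biopsy and array cores will be noisier. Density has its own weakness: if tissue shrinks after SBRT to 80% of its area (assumption) with the count unchanged, density rises by 1 / 0.8 = 1.25. Reporting the supportive percentage beside it helps the reader to judge such shifts, but does not remove them.
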